PARTNERS HUMAN RESEARCH COMMITTEE PROTOCOL SUMMARY

Answer all questions accurately and completely in order to provide the PHRC with the relevant information to assess the risk-benefit ratio for the study. Do not leave sections blank.

PRINCIPAL/OVERALL INVESTIGATOR

[name]

PROTOCOL TITLE

Upper extremity rehabilitation with the BURT robotic arm: a feasibility study.

FUNDING

Barrett Technology, Inc.

VERSION DATE

October 5, 2018 - Amendment 1

SPECIFIC AIMS

Concisely state the objectives of the study and the hypothesis being tested.

PRIMARY:

 To assess the feasibility of the BURT robotic device to deliver upper extremity training with focus on the system control and error feedback modalities suitable for running long-term interventions. The study will be performed in a small cohort of stroke survivors with impaired upper extremity function.

For example, we would like to assess if the device can be used to achieve the desired range of motion for post-stroke rehabilitation of upper extremity. We would also like to assess if stroke patients are able to follow the instructions provided by the software application and whether the device is easy to use from the therapist's perspective.

SECONDARY:

 Gather usability and design-evaluation feedback sessions with clinical personnel and stroke survivors involved in the study.

BACKGROUND AND SIGNIFICANCE

Provide a brief paragraph summarizing prior experience important for understanding the proposed study and procedures.

Stroke is a leading cause of disability among older adults afflicting nearly 800,000 people each year in the US alone. Roughly half of stroke survivors suffer from chronic hemiparesis. Limited motor recovery in the paretic upper limb accounts for a large proportion of the disabling sequelae. Only about 15% of those with initial complete upper limb paralysis after stroke recover the functional use of their impaired arm in daily life.

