Motor training is associated with motor recovery and cortical plasticity. High-intensity, task-specific training leads to greater motor gains than conventional therapy. Virtual reality and robotics are technologies that are suitable to facilitate the implementation of interventions marked by high intensity and task specificity. Recent research has identified several key features of training using a virtual environment that facilitate motor skill reacquisition. These features include high intensity of motor practice, training in stimulating environments thus offering high motivation to the subject, and enhanced feedback (visual and auditory) about the performance of the motor task.

Robotic devices for upper-limb rehabilitation have been shown to improve upper limb function. Transfer of learned movements to functional tasks has been observed in stroke survivors following robot-assisted motor training. Subjects undergoing upper limb robot-assisted rehabilitation generally show larger motor gains than subjects undergoing conventional therapy. The combination of virtual reality and robotics provides clinicians with the means to implement implicit learning paradigms, which have been shown to be particularly effective in rehabilitation.

The overall objective of the proposed study is to carry out usability and design-evaluation assessments of the BURT robotic device for delivering long-term intervention in stroke survivors. The BURT is an upper extremity robotic device that enables the user to see and feel engaging games that encourage intensive therapy. It has 510-K FDA clearance. The device itself provides a significant range of motion designed to match the range of motion in the shoulder joint. The games help motivate the user and can be programmed to become progressively harder as the therapy progresses.

Figure 1 –BURT System (image courtesy of Barrett Medical http://www.barrettmedical.com/)

RESEARCH DESIGN AND METHODS

Briefly describe study design and anticipated enrollment, i.e., number of subjects to be enrolled by researchers study-wide and by Partners researchers. Provide a brief summary of the eligibility criteria (for example, age range, gender, medical condition). Include any local site restrictions, for example, "Enrollment at Partners will be limited to adults although the sponsor's protocol is open to both children and adults."

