We intend to recruit up to 10 stroke survivors over the course of the study. The stroke survivors will participate in a question and answer formatted discussion with research staff to discuss the usability of the device. The clinical personnel involved in the study will participate in a voluntary feedback session to discuss the usability of the device from a clinician's perspective. We will gather feedback from the clinicians about the device. Due to the voluntary nature of the feedback gathered from clinical personnel, consent will be assumed with participation.

We plan to recruit up to 10 stroke survivors based on the following inclusion/exclusion criteria.

Inclusion Criteria

- 1. Male and female, age 18-80;
- 2. Having had a stroke (ischemic or hemorrhagic) at least 6 months prior to study enrollment:
- 3. Moderate to severe upper-limb motor impairments: score of 15-45 out of 66 on the Fugl-Meyer Scale;
- 4. Community dwelling;
- 5. Able to physically fit in the device.

Exclusion Criteria

1. Current participation in rehabilitation program targeting upper extremity function;

- 2. Cognitive impairment resulting to inability to follow instructions (MMSE ≥ 23 and subject is able to follow the 3-Stage Command) or inability to sustain attention for more than 10 minutes:
- 3. Visual impairments as assessed by the NIH Stroke Scale Visual Field subscale (only subjects with no visual loss will participate in the study);
- 4. Aphasia sufficient to limit comprehension and completion of the treatment protocol;
- 5. No more than moderate impairments in paretic UE sensation, passive range of motion, and pain that would limit ability to engage in therapy;
- 6. Increased muscle tone as indicated by score of >/= 3 on the Modified Ashworth Scale;
- 7. Previous diagnosis of neurological diseases other than stroke;
- 8. Other conditions affecting function of the stroke affected upper limb;
- 9. Individuals who present with the following:
 - open wounds
 - fragile skin
 - active infection

Briefly describe study procedures. Include any local site restrictions, for example, "Subjects enrolled at Partners will not participate in the pharmacokinetic portion of the study." Describe study endpoints.

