Informed consent will be obtained by study staff members who have completed the Partners Healthcare System's human subject protection educational requirements, and the CITI Program in Protection of Human Subjects, in compliance with all Federal regulations regarding such training. Prospective subjects will be interviewed to determine preliminary eligibility. Informed consent will be obtained and subjects will be enrolled in the study prior to any clinical or laboratory testing. Subjects will be given a copy of the IRB approved consent form during the initial interview, and study staff will explain in detail the nature of the informed consent process, study purpose and procedures, time commitments, risks, potential benefits, treatment alternatives, rights as research participants, study staff contact information, confidentiality

procedures, and arrangements for medical care provided in case of injury during the study. Participants will be provided with a signed copy of the completed consent form.

• Visit number 2:

Baseline outcomes assessment battery. The clinical assessment session will last approximately $1 \frac{1}{2}$ to 2 hours. A battery of standardized measures for upper extremity in stroke rehabilitation will be administered. The battery will include: (1) range of motion and muscle strength assessment, (2) spasticity evaluation with the Modified Ashworth Scale, (3) Fugl-Meyer Assessment of upper extremity including pain and sensation subtests, (4) Wolf Motor Function Test and (5) the Motor Activity Log. All are reliable and valid measures of upper extremity motor capacity and function. We will also use the Goal Attainment Scaling to identify specific goals to focus on during the intervention. The Fugl-Meyer is our primary outcome measure and the Goal Attainment Scale our secondary outcome measure. The remaining outcome measures will be exploratory.

• Visit number 3-20:

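### The aims put BURT feasibility first and usability second, but the only outcome ranking names the Fugl-Meyer and the Goal Attainment Scale, so neither aim has a primary or secondary outcome that measures it

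*Protocol*

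**What the plan says.** **Aims.** In the Protocol, Specific Aims, the primary aim is "To assess the feasibility of the BURT robotic device to deliver upper extremity training with focus on the system control and error feedback modalities". The examples that follow concern the device in use: "we would like to assess if the device can be used to achieve the desired range of motion", whether patients can follow the software's instructions, and whether therapists find the device easy to use. The secondary aim is "Gather usability and design-evaluation feedback sessions with clinical personnel and stroke survivors involved in the study".

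**Objective restated.** Background and Significance says "The overall objective of the proposed study is to carry out usability and design-evaluation assessments of the BURT robotic device". Expected Benefits again calls this a usability study.

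**Outcomes.** In Research Design and Methods, the form's prompt for the procedures section ends with "Describe study endpoints". The only ranking in the answer comes under Visit number 2, after the list of clinical tests: "The Fugl-Meyer is our primary outcome measure and the Goal Attainment Scale our secondary outcome measure". The next sentence makes the other outcome measures exploratory.

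**Data bearing on the aims.** Research Design and Methods provides that "The stroke survivors will participate in a question and answer formatted discussion with research staff to discuss the usability of the device" and that "The clinical personnel involved in the study will participate in a voluntary feedback session to discuss the usability of the device". The list of data sources includes the robot's embedded sensors and feedback surveys. Visit number 3-20 includes a workspace measurement at the first treatment session. Visit number 21 adds a visual analogue scale (VAS) questionnaire for participants and clinical staff. None of these is called primary or secondary.

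**The concern.** A primary outcome should answer the primary question. Here the question is whether the device can deliver the training and how users find it, while the measures ranked first and second describe the participant's arm function and personal goals. A Fugl-Meyer score could rise with a device that is awkward to control, or stay flat with one that works smoothly.

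At stake is what the study reports first. If the ranking is applied to the whole study, the lead results are before-after changes in a motor score and a goal score. The evidence on control, error feedback and ease of use then follows with no stated priority. This is not detail that can wait for an analysis plan: the Protocol already states a ranking, and a plan that followed it would carry the mismatch forward.

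**Working it through.** No arithmetic decides this point. The Protocol states no power or sample-size calculation to reproduce, and up to 10 participants is a cap without a derivation. The check is to set the sections side by side.

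**Step 1: match aims to outcomes by rank.**

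| Rank | Aim (Specific Aims) | Outcome (Visit number 2) | Does the outcome measure the aim? |
|---|---|---|---|
| Primary | Feasibility of the device, with control and error feedback in focus | Fugl-Meyer | No: it scores the participant's impairment |
| Secondary | Usability and design feedback | Goal Attainment Scale | No: it scores the participant's own goals |

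Matches: 0 of 2. Neither aim mentions change in motor impairment or in goal attainment.

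**Step 2: find the data that bear on the aims, and their rank.**

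| Data | Where described | Bears on | Named primary or secondary? |
|---|---|---|---|
| Robot sensor data | Data sources | Feasibility (an inference: the Protocol does not say what the sensors record) | No |
| Workspace measurement | Visit number 3-20 | Movement reached with the device | No |
| VAS questionnaire: set-up, comfort, error display, haptic feedback, exercise types, clarity of instructions | Visit number 21 | Both aims | No |
| Participant discussion and clinician session | Research Design and Methods | Secondary aim, directly | No |

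The clinical battery also contains a range-of-motion test. It is at most exploratory and examines the participant, whereas the aim asks what can be achieved with the device.

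**Step 3: try both readings of the ranking.**

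- *Study-wide.* The Fugl-Meyer leads the study and the usability data fall among the exploratory measures. This contradicts the aims.
- *Clinical battery only.* There is no direct contradiction, but the primary aim then has no named outcome, although the form asked for endpoints.

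Both readings leave the primary aim without an outcome. They differ in what must happen to the Fugl-Meyer: only the first requires it to give up a study-wide rank.

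**Step 4: what a change in the clinical scores would describe.** Each scheduled session has 30 minutes with the robot and 30 minutes of hands-on training. Over 18 sessions that is 18 × 30 = 540 minutes, or 9 hours, of each. There is no comparator, so a before-after change follows the combined programme. This affects how the scores should be described; it is not what makes the ranking wrong.

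**The case against.** The strongest reply is that the ranking sentence closes a paragraph about the baseline battery, directly after the clinical tests, and that the questionnaire appears only later, at Visit number 21. Read that way, the sentence merely orders the clinical tests. This is a plausible reading and it removes the outright contradiction. It does not supply an outcome for the primary aim, so a repair is still needed, though a lighter one.

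A second reply is that the usability data are all planned, from two groups of raters and with room for free comments. That stands. A reader might infer that these data would be lost or left unreported; the Protocol does not support that. What is missing is their priority.

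Third, motor benefit is part of the stated interest: Expected Benefits hopes that more than 25% of participants will show better functional use of the arm. That also stands, but it is a hoped-for benefit and not an aim. It justifies keeping the scales, and it leaves the sponsor free to add motor change to the aims.

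Fourth, a reader might infer that the small sample, the lack of a comparator or the mixed sessions make the Fugl-Meyer unfit to be primary. These belong to a single-arm feasibility design. With at most 10 participants, precision is limited for a VAS item just as for a Fugl-Meyer change, so it favours neither ranking.

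**Conclusion.** The point holds as a mismatch between ranked aims and ranked outcomes. Neither of the two ranked outcomes measures either of the two aims, and no measure of feasibility or usability is named primary or secondary. It rests on the Protocol's wording alone and needs no assumed figure.

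Two limits apply. A reader might infer that the Fugl-Meyer must be demoted whatever the sentence meant. The text does not support that: on the battery-only reading it can stay first among the clinical tests, provided a feasibility outcome is named above them. Nor does the Protocol settle what will be reported first. The misplaced headline is the consequence of applying the ranking study-wide, not something the document states.

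This should be corrected, because the change is cheap and lets the study answer its own question. No result is invalidated by it.

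**What to change.** Under Visit number 2, say what the ranking covers and align it with the Specific Aims:

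- **Primary: a descriptive feasibility set, with no test.** (a) Workspace or range of motion reached with the device, from the workspace measurement, or from the sensors if they record it. (b) Sessions delivered out of 18. (c) The VAS items on error display, haptic feedback, clarity of instructions and ease of set-up. (d) A VAS item on control modality, added to the existing questionnaire because the primary aim names system control; the topics listed at Visit number 21 are examples and none of them covers it.
- **Secondary.** The remaining questionnaire items and the feedback sessions, from participants and clinical staff.
- **Leading clinical (exploratory) measures.** The Fugl-Meyer and the Goal Attainment Scale, reported as before-after change following the combined robot plus hands-on programme.

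If the sponsor does want motor change as a primary outcome, the Specific Aims must state it as an aim, and feasibility still needs an outcome of its own.

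**Cost.** Some rewording, a short definition of the workspace or range-of-motion summary, and one questionnaire item; no new visit or clinical test. Sessions must be counted already, since participants are paid per training session.

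**Downsides.** The Fugl-Meyer loses headline status. The feasibility estimates come from at most 10 participants and an unstated number of staff raters, so they will be imprecise and descriptive, with no pass mark. The questionnaire is given only at visit 21. Rated clarity of instructions is a proxy for being able to follow them, and ease of set-up is narrower than ease of use for the therapist.

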Intervention. Participants will receive robot-assisted upper extremity research therapy using the BURT (figure 1, page 1). The BURT provides position-controlled exercises during computerized games that emphasize repetitive movements of the paretic upper extremity. Rest periods will be offered between games, as needed. During the first treatment session, the BURT will be adjusted for the participant's arm size and the workspace will be measured via standard procedures. Subjects will be instructed to perform a series of motor tasks using the BURT system. All tasks will be performed in a seated position. Arm movements will be remapped into a virtual environment and displayed on a computer screen to enable feedback. The motor tasks to be performed by subjects will consist of arm movements aimed at performing an "activity" in the virtual environment (e.g. picking up a box, scrubbing a surface, drawing simple geometric shapes, ...). The interaction between the subject and the BURT system will be set using either cooperative or competitive control strategies. Augmented feedback modalities (i.e. the application of gains to "magnify" aspects of the display of error-related information) will be tested. Also, the selected set of games will allow us to test different feedback modalities (e.g. visual and auditory cues) and different control modalities. Task challenge for each training device will be incrementally increased or decreased based on participant performance.

All participants will receive 1 hour sessions, 2-3x/week for 6 weeks (total 18 sessions). Sessions will be organized with 30 minutes of robotic-assisted training and 30 minutes of hands-on training with a research therapist to work on the baseline goals of the subject. Hands-on training will be done with routinely employed techniques in therapy to transfer the skills gained with the robotic device in everyday life activities.

Participants may miss up to 3 appointments, and we will reschedule the following day or week at a time that is mutually convenient. Participants who miss 4 consecutive appointments may be removed from the study.

• Visit number 21:

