End-of-intervention outcomes assessment battery. We will repeat the same battery as performed in study visit number 2. Additionally, we will gather qualitative feedback under the form of a questionnaire in regard to the usability and the design characteristics of the device (the same questionnaire will be to study volunteers and study staff with clinical expertise (e.g. therapists and physiatrists)). The content of the questionnaires will be focused on aspects of the BURT system design such as the following: the ease of setting up the system; the comfort level achieved by the design of the human-robot interface; the effectiveness of the visual display of error feedback; the intuitiveness of the haptic feedback; the types of therapeutic exercises enabled by the system; the clarity of the instructions provided to guide the performance of

exercises. Feedback will be gathered using a visual analogue scale. We will also take note of any other comments study participants and study staff with clinical expertise might have. Study staff will guide the subject thru the questionnaire and be readily available to answer any question.

Assessments: Baseline

18 sessions:
Robotic-assisted upper extremity training

Assessments: End-of intervention

Schema 1: study procedures flow

For studies involving treatment or diagnosis, provide information about standard of care at Partners (e.g., BWH, MGH) and indicate how the study procedures differ from standard care. Provide information on available alternative treatments, procedures, or methods of diagnosis.

Standard of care for individuals with chronic motor impairments >6 months' post stroke does not typically involve upper extremity rehabilitation. However, individuals with stroke may at times be involved in standard occupational therapy intervention to address upper extremity motor impairments and optimize functioning during basic activities of daily living (ADL) and instrumental ADLs (e.g. cooking, shopping etc.). The study interventions differ from standard care in that robot training activities provide a much higher number of movement repetitions than is possible during conventional rehabilitation practice.

Describe how risks to subjects are minimized, for example, by using procedures which are consistent with sound research design and which do not unnecessarily expose subjects to risk or by using procedures already being performed on the subject for diagnostic or treatment purposes.

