The criteria for continued participation and participant removal from the study are as follows: we will allow participants to miss up to 3 appointments and will reschedule the following day or week at a time that is mutually convenient. We will remove participants from the study after 4 consecutive missed appointments.

In case in which a subject experiences discomfort they will be free to remove the system and end their participation in the study.

Videos of the sessions will be locked in cabinets and on password protected encrypted computers.

FORESEEABLE RISKS AND DISCOMFORTS

Provide a brief description of any foreseeable risks and discomforts to subjects. Include those related to drugs/devices/procedures being studied and/or administered/performed solely for research purposes. In addition, include psychosocial risks, and risks related to privacy and confidentiality. When applicable, describe risks to a developing fetus or nursing infant.

• The BURT is equipped with actuated components (i.e. motors) capable of independent motion. Risks are minimal when the BURT is used according to instructions. Small injuries, such as bruising or stretching can occur in rare cases, however, numerous safety features and procedures have been implemented to minimize risk of injury. These include a system controller designed to avoid excessively fast movements of the upper extremity joints; safety limits set for the estimated interaction forces during arm motions, and two emergency switches to immediately shut off robot power in the event of a malfunction. Height adjustments of the BURT will be performed with caution so injury does not occur when

lowering the device to ensure proper positioning for therapy. The straps of the device may cause redness of the skin. We will assure proper upper limb positioning during intervention and will pad the straps as needed so they are comfortable for the subject. Performing the tasks may cause muscle soreness similar to the potential soreness from normal daily activities.

 Being videotaped poses a privacy risk. These videos could be seen by people outside of the study staff who may be able to recognize your face. We will lock these videos in cabinets and on password protected encrypted computers that only study staff associated with the study can access.

EXPECTED BENEFITS

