Since it is relatively common for people to have impaired decision-making capability after a stroke, prospective study volunteers' decision-making capacity and ability to give consent will be assessed using the University of California at San Diego Brief Assessment of Consent Capacity (UBACC) Questionnaire. If the subject demonstrates that he/she is able to understand the study procedures and provide consent, we will proceed to obtain informed consent. In the event that a potential subject fails the UBACC and a surrogate is not present, we will ask the subject's permission to contact a surrogate over the phone. The consenting process will be stopped until both, subject and surrogate, are present. We will contact the surrogate, ask if they would be willing to come to the laboratory with the subject and make an appointment if they agree. We will go over the consent form in detail with the surrogate and provide them sufficient time to go over the study, ask questions and make an informed decision.

Study staff members (either the PI or a non-clinician investigator not involved in the patient's care) who have completed the human subject protection educational requirements, and the CITI Program in Protection of Human Subjects, in compliance with all Federal regulations regarding such training, will obtain informed consent in the Motion Analysis Laboratory (MAL) at SRH. The test procedures will be described to the subject. Study staff will clearly explain all the procedures and risks of the testing outlined in the informed consent form (ICF). The subject will be told that the informed consent also asks for permission to view information in their medical records (for instance images) to gain a better understanding of the characteristics of their stroke (e.g. site and severity of their stroke). They will also be told that the investigators will limit their review to already existing head CT and MRI images and reports already contained in the Electronic Medical Record system. The subject will be given adequate time to consider their decision to participate in the study and encouraged to ask questions, both during the initial interview and throughout the study. A member of the study staff will answer any questions regarding the study

at the time consent is given. Once enrolled, the subject may pause or terminate his/her participation at any time during the study.

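### The participant usability questionnaire is scheduled only at Visit 21, so those who stop earlier, including for discomfort, leave no rating

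*Protocol*

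**What the plan says.** Specific Aims lists usability and design feedback from clinicians and stroke survivors as the secondary aim. Background and Significance gives it more weight: "The overall objective of the proposed study is to carry out usability and design-evaluation assessments of the BURT robotic device".

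In Research Design and Methods, the participant questionnaire appears in the visit schedule once, under Visit number 21: "Additionally, we will gather qualitative feedback under the form of a questionnaire in regard to the usability and the design characteristics of the device". It is answered on a visual analogue scale, and one of its topics is "the comfort level achieved by the design of the human-robot interface". The entries for Visits 1, 2 and 3–20 contain no usability questionnaire. Schema 1 shows baseline assessments, 18 sessions and end-of-intervention assessments, with no exit step.

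The protocol allows three routes out before Visit 21:

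- Discomfort (criteria for continued participation and removal): "In case in which a subject experiences discomfort they will be free to remove the system and end their participation in the study".
- Missed appointments (same paragraph): "We will remove participants from the study after 4 consecutive missed appointments".
- Free choice (Consent Procedures): "Once enrolled, the subject may pause or terminate his/her participation at any time during the study".

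Two other sources of participant feedback are mentioned without a time point. One is a conversation described with the recruitment plan: "The stroke survivors will participate in a question and answer formatted discussion with research staff to discuss the usability of the device". The other is the feedback surveys in the list of data sources at the start of the study procedures.

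**The concern.** Comfort is both a topic that participants rate and a reason the protocol names for leaving. Someone who leaves because the device is uncomfortable would probably rate comfort, and perhaps usability in general, lower than someone who completes all 18 sessions. If the form is given only at Visit 21, these are the ratings most likely to be absent.

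The participant ratings could then look better than the experience of everyone who started training. For a study meant to judge whether the device suits long-term interventions, the views of people who could not or would not continue are among the most useful. When a form is given is fixed by the protocol. An analysis plan can count the missing ratings, but it cannot recover answers that nobody asked for.

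**Working it through.** The protocol gives no dropout rate, no scale range for the questionnaire and no target for the ratings, so it has no figure of its own to reproduce. The check is a comparison of passages, followed by illustrations whose assumptions are marked.

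**Step 1. When is a participant rating collected?**

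| Stage | Participant usability questionnaire |
|---|---|
| Visit 1 (consent, screening) | none |
| Visit 2 (baseline battery) | none |
| Visits 3–20 (training) | none |
| Visit 21 (end of intervention) | yes |
| Leaving for discomfort | none described |
| Leaving by choice | none described |
| Removal for missed appointments | none described |

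The remuneration list agrees: up to 2 assessment sessions at $50 and up to 18 training sessions at $5, so 2 × 50 + 18 × 5 = $190, the stated maximum. No exit contact is listed.

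**Step 2. Could another source supply the rating?**

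- The question-and-answer discussion has no time point, is not a scale rating and is not extended to leavers.
- The feedback surveys in the data-source list have no time point of their own. The only scheduled administration is at Visit 21.
- Pain and discomfort reports during sessions go to the investigator for medical decisions. They are not ratings and do not cover the display, haptic feedback or instructions.
- Staff complete the same questionnaire, but that gives the staff's view.

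**Step 3. Share of questionnaires lost.** The planned maximum is N = 10 (Research Design and Methods). If 10 start training, each leaver removes 1/10 = 10% of the participant questionnaires. The share is larger if fewer start.

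**Step 4. How far could the mean move?** Let C be the mean rating of completers, L the mean that leavers would have given, and d the number of leavers. The mean over all starters is [(N − d)C + dL]/N, so

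completer mean − all-starter mean = (d/N) × (C − L).

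With N = 10, an assumed 0–100 scale and assumed gaps C − L:

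| Leavers d | Gap 20 points | Gap 50 points |
|---|---|---|
| 1 | 0.1 × 20 = 2 | 0.1 × 50 = 5 |
| 2 | 0.2 × 20 = 4 | 0.2 × 50 = 10 |
| 3 | 0.3 × 20 = 6 | 0.3 × 50 = 15 |

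If leavers would have rated no lower than completers, the mean is not overstated.

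**Step 5. How likely is at least one lost form?** With an assumed leaving chance p per participant, and participants independent, the chance is 1 − (1 − p)^10:

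- p = 5%: 1 − 0.5987 = 40%, with 10p = 0.5 lost on average
- p = 10%: 1 − 0.3487 = 65%, with 1 lost on average
- p = 20%: 1 − 0.1074 = 89%, with 2 lost on average

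These are chances of losing a form under assumed rates. They do not measure bias.

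**The case against.** The best reply is that this is silence in a short ethics-committee summary form, not a misstatement. Nothing in the protocol forbids asking leavers for feedback, and the usability discussion is stated for the stroke survivors without a condition of completion. That much stands: a reader might infer that early leavers will not be heard at all, and the text does not support this. Comments from some of them are possible; the protocol simply does not ensure them. The point is therefore confined to the scheduled questionnaire ratings. For those, the timing is specified, and it is a timing that misses leavers.

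A second reply concerns weight. Specific Aims makes usability feedback the secondary aim, and the Visit 2 text makes the Fugl-Meyer the primary outcome and Goal Attainment Scaling the secondary one. This also stands. From the words about the overall objective in Background and Significance, a reader might infer that the study's primary result is at risk. The documents do not support that, since the gap concerns the usability ratings alone.

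Third, the protocol calls the feedback qualitative and sets no threshold or decision rule on it. In a cohort of at most 10, a withdrawal for discomfort would be visible as an event, through symptom reporting and the investigator's monthly review. This limits the harm: the fact of withdrawal is not hidden. It does not supply the missing rating.

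Finally, removal for missed appointments need not have anything to do with comfort, so not every lost form would be informative. That is correct, and it is one reason why the size cannot be stated.

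**Conclusion.** The point holds in a limited form. The only scheduled participant rating of usability and comfort comes at Visit 21, and the routes out before that visit carry no exit rating. Participant ratings would come from completers only and could favour the device.

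The direction rests on one assumption, which is plausible but not documented: that people who leave because of discomfort would have rated the device lower. The size is unknown. The shifts of 2 to 15 points and the chances of 40%, 65% and 89% depend on assumed gaps, an assumed scale and assumed leaving rates. A reader might take the percentages as the probability or extent of a biased result; they show only how easily one form is lost among 10. If everyone completes, the gap has no effect.

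It is worth correcting because it touches the usability aim, cannot be repaired afterwards and is cheap to close. It does not invalidate the study.

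Separately, the two statements on four consecutive missed appointments disagree. The Visit 3–20 text says "Participants who miss 4 consecutive appointments may be removed from the study", whereas the removal criteria make removal definite (quoted above). A reader might infer that this conflict worsens the questionnaire gap. It does not: under either wording, nobody who leaves is offered the form.

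**What to change.** Under Visit number 21, add that the same questionnaire is offered, on a voluntary basis, to everyone who started training and then stops or is removed, either at last contact or by phone with the participant's agreement. Add that ratings will be shown beside the number who started training and the number of ratings missing. The second sentence could equally go in an analysis plan; the first has to be in the protocol, because it governs what is collected.

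The cost is a sentence or two of text and one short contact per leaver, using the existing form. Completers carry no added burden and the training sessions do not change. Some leavers will decline, so the gap may narrow without closing.

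As a separate correction, the statements on four consecutive missed appointments, in the Visit 3–20 text and in the removal criteria, must be reconciled. Which wording applies is for the investigator to decide.
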